1.1 Epidemiological background of glioblastoma

Brain glioma refers to a tumor originating from brain glial cells and is the most common primary intracranial tumor[1]。The 2021 edition of the WHO Central Nervous System Tumor Classification categorizes gliomas into grades 1-4, with grades 1 and 2 being low-grade gliomas and grades 3 and 4 being high-grade gliomas. The incidence rate of brain glioma in China is 5-8/100000, and the 5-year mortality rate is only second to pancreatic cancer and lung cancer in general tumors. Gliomas have high disability and recurrence rates, posing a serious threat to patients' lives, affecting their quality of life, and imposing heavy psychological and economic burdens on individuals, families, and even society.

Glioblastoma (GBM) is a high-grade brain glioma classified as WHO grade 4. It is the most common primary malignant tumor in adult central nervous system tumors, accounting for approximately 57% of all gliomas and 48% of all primary central nervous system malignancies[2]。GMB is the most invasive malignant brain tumor with a poor prognosis, with a 1-year survival rate of approximately 40.6% and a 5-year survival rate of only 5.6%[3]。

1.2 Standard treatment for newly diagnosed glioblastoma

The treatment for newly diagnosed GBM mainly involves surgical resection of the tumor, combined with comprehensive treatment methods such as radiotherapy and chemotherapy. The combination of tumor resection within the maximum safe range, postoperative radiation therapy involving the field, and

concurrent and adjuvant Temozolomide (TMZ) chemotherapy (Stupp regimen) is the standard first-line treatment for newly diagnosed GBM[4]。 The median overall survival (OS) of newly diagnosed GBM patients treated with Stupp regimen was 14.6 months, with a 2-year OS rate of 26.5% and a 2-year PFS rate of 10.7%. Unlike the Stupp regimen, which started oral administration of TMZ on the first day of radiotherapy, the neurosurgery department of Huashan Hospital in Shanghai conducted a multicenter clinical study (START regimen) using TMZ chemotherapy in the early postoperative period (2 weeks after surgery) of GBM, followed by synchronous radiotherapy and chemotherapy. The results showed that the median OS of the START regimen group could reach 17.6 months, which was significantly better than the Stupp regimen[5]。 According to the 2024 NCCN, SNO-EANO, and the Chinese Guidelines for the Diagnosis and Treatment of Gliomas (2022 edition), surgery, postoperative radiotherapy, and TMZ chemotherapy are currently the standard treatment options for newly diagnosed GBM. However, even with standard treatments such as surgery and chemotherapy, the median OS of GBM patients is about 15-18 months, and the 5-year OS rate is still less than 10%. Once GBM recurs, the median OS is estimated to be only 24-44 weeks. Therefore, exploring how to improve treatment efficacy and prognosis is of great significance for GBM patients.

1.3 Progress in the treatment of newly diagnosed glioblastoma

In recent years, in order to further improve the prognosis of GBM patients, multiple clinical studies have been continuously exploring the optimal comprehensive treatment plan for newly diagnosed GBM, including extending the time of TMZ adjuvant chemotherapy, combining other chemotherapy drugs, combining anti vascular drugs, combining immunotherapy, and electric field therapy. Simultaneous chemoradiotherapy combined with TMZ adjuvant chemotherapy for 6 cycles is the standard treatment regimen for GBM patients. A phase II randomized GEINO14-01 clinical study explored whether prolonging the TMZ adjuvant therapy cycle could improve patient prognosis. A total of 159 patients were analyzed in the study, with the control group receiving the standard Stupp regimen and the experimental group receiving TMZ chemotherapy for more than 6 cycles. The results showed no significant difference in PFS and OS between the two groups at 6 months[6]。

Several clinical studies have explored the efficacy of combination therapy based on the Stupp regimen. AVAglio clinical studies have shown that the combination of bevacizumab, radiotherapy, and TMZ treatment prolongs median PFS by 4.4 months in newly diagnosed GBM patients, but does not improve overall survival[7]。 A randomized open label Phase III CeTeG/NOA-09 clinical trial initiated by the Neuro Oncology Working Group of the German Society of Oncology analyzed the application value of the combination of lomustine and TMZ in the treatment of GBM patients. The results showed that the combination of the two could achieve a total OS of 48.1 months for GBM patients with MGMT gene promoter methylation, while using TMZ alone was only 31.4 months [8]。 On the basis of the Stupp protocol, electric field therapy (TTF) was added during the assisted TMZ period, which extended the median OS of newly diagnosed GBM patients by 4.9 months and increased the 5-year survival rate to 13%[9]。 Based on preclinical studies showing significant efficacy of anti-CTLA-4 and anti-PD-1

combination immunotherapy in a GBM model, a phase I clinical study NRG-BN002 evaluated the safety of immune checkpoint inhibitors alone or in combination for newly diagnosed GBM. The combination immunotherapy of anti-CTLA-4 and anti-PD-1 has good tolerability and safety, with median OS and PFS of 20.7 months and 16.1 months, respectively[10], The therapeutic effect is superior to the standard Stupp regimen. This research result supports the subsequent phase II/III clinical trials of combined immunotherapy for newly diagnosed GBM patients. The above clinical research data suggests that the combination of TMZ and other treatment methods can improve patient prognosis to a certain extent.

In addition, considering that radiotherapy is an independent factor affecting the survival of GBM patients, exploring whether increasing the intensity of radiotherapy can further improve the prognosis of GBM patients has always been an important area of clinical research. Multiple exploratory studies based on metabolic imaging guidance on whether local high-dose radiation therapy can improve patient prognosis. A meta-analysis of 22 prospective clinical studies showed that increasing the radiation dose to between 62.5Gy and 80Gy did not significantly improve patient prognosis compared to the standard dose of 60Gy[11], It may be related to the failure to distinguish between complete resection and partial resection or short-term recurrence patients, as well as the increased side effects of radiotherapy in high-dose areas including the entire tumor bed. Therefore, administering low-dose radiation to residual or recurrent lesions alone, and administering current standard dose radiation therapy to tumor beds and high-risk areas for recurrence, may further improve the survival benefits of GBM patients while controlling adverse reactions to radiation therapy.

1.4 Patients with partial surgical resection or short-term recurrence and progression of GBM have a worse prognosis

The degree of surgical resection is an independent factor for predicting the prognosis of GBM patients[12]。A retrospective analysis of the impact of surgical resection degree on prognosis in 500 newly diagnosed GBM patients showed that the OS of patients with 100% resection, 90% resection, 80% resection, and 78% resection were 16 months, 13.8 months, 12.8 months, and 12.5 months, respectively[13]。 This study suggests that patients undergoing partial surgical resection or short-term postoperative recurrence and progression require stronger postoperative adjuvant therapy to further improve survival. However, currently there are no clinical studies on postoperative adjuvant therapy for patients with GBM who have undergone partial surgical resection or short-term recurrence and progression before postoperative radiotherapy, which are consistent with those who have undergone total surgical resection. Therefore, further prospective clinical studies are needed to explore the benefits of intensified adjuvant therapy in patients undergoing partial surgical resection or short-term postoperative recurrence and progression.

In summary, in newly diagnosed GBM patients undergoing partial surgical resection or short-term recurrence progression, studying the benefits of intensified adjuvant therapy on PFS rate, OS rate, quality of life, and other aspects based on the Stupp regimen can help further optimize the comprehensive treatment plan for GBM patients. Here, we conduct a prospective Bayesian adaptive randomized controlled

clinical study. Unlike traditional randomization methods, Bayesian adaptive randomization can continuously update probability estimates during the trial to better utilize trial data and dynamically adjust randomization ratios or intervention strategies based on trial results, providing a basis for the optimal comprehensive treatment selection for more GBM patients.

2.1 Main research objectives

Evaluate the effect of intensified adjuvant therapy on the 3-month, 6-month, and 12-month PFS rates in newly diagnosed GBM patients undergoing partial surgical resection or short-term recurrence progression (using RANO 2.0 criteria).

2.2 Secondary research objectives

2.2.1 Evaluate the impact of intensified adjuvant therapy on 1-year and 2-year overall survival rates and quality of life in patients with newly diagnosed glioblastoma who undergo partial surgical resection or short-term recurrence progression.

2.2.2 Evaluate the safety and incidence of radiation necrosis in newly diagnosed glioblastoma patients undergoing enhanced adjuvant therapy with surgical partial resection or short-term recurrence progression.

3, Research design and methodology:

3.1 Research overall design

This study is a prospective, randomized, controlled, open label, single center phase II study that uses Bayesian adaptive randomization to assess the efficacy and safety of intensified adjuvant therapy in newly diagnosed GBM patients undergoing partial surgical resection or short-term recurrence progression, based on the Stupp standard treatment regimen. Newly diagnosed GBM patients who undergo partial surgical resection or short-term recurrence progression (2-6 weeks after surgery before radiotherapy), after signing informed consent forms, will be screened to meet inclusion and exclusion criteria. In the first stage of Bayesian adaptive randomization, qualified subjects will be stratified and randomized in a 1:1:1:1 ratio to Stupp group, Stupp+PD-1/VEGF bispecific group, Stupp+PD-1/CTLA-4 bispecific group, and modified Stupp group with adjusted radiotherapy dose. In the second stage of Bayesian adaptive randomization, probability estimates are continuously updated based on the efficacy evaluation results of each group in the first stage, and the proportion of individuals randomized to each treatment group is dynamically

adjusted according to the trial results. A new round of randomization is conducted for each group of 16 individuals. The four treatment plans are as follows:

Stupp group: Synchronized TMZ radiotherapy and chemotherapy will begin 2-6 weeks after surgery, and 6 cycles of adjuvant TMZ chemotherapy will begin 28 days after completing the synchronized radiotherapy and chemotherapy. Radiotherapy regimen: PTV1 60Gy/30F in high-risk areas around the tumor bed, 54Gy/30F in low-risk areas. TMZ synchronous chemotherapy regimen: 75mg/m² po qd. TMZ adjuvant chemotherapy regimen: The first cycle is 150mg/m² po qd on d1-5,28 days; Cycle 2-6: Cycle 1: 200mg/m² po qd for d1-5,28 days.

Stupp+PD-1/VEGF dual antibody group: Starting 2-6 weeks after surgery, synchronous TMZ radiotherapy and chemotherapy will be performed. After completing synchronous radiotherapy and chemotherapy for 28 days, TMZ combined with PD-1/VEGF dual antibody will be used as adjuvant therapy. PD-1/VEGF dual antibody 20mg/kg intravenous infusion once, with a cycle of 21 days.

[figure not shown]
Stupp+PD-1/CTLA-4 dual antibody group: Starting 2-6 weeks after surgery, synchronous TMZ radiotherapy and chemotherapy will be performed. After completing synchronous radiotherapy and chemotherapy for 28 days, TMZ combined with PD-1/CTLA-4 dual antibody will be used as adjuvant therapy. PD-1/CTLA-4 dual antibody 6mg/kg intravenous infusion once, with a cycle of 14 days.

Modified Stupp group: Starting 2-6 weeks after surgery, synchronous TMZ radiotherapy and chemotherapy will be performed. For partially resected lesions or short-term recurrence and progression lesions after surgery, high-dose PGT 66Gy/30Gy will be given locally. PTV1 in high-risk areas around the tumor bed will be 60Gy/30F, and in low-risk areas will be 54Gy/30F. After completing synchronous radiotherapy and chemotherapy for 28 days, 6 cycles of adjuvant TMZ chemotherapy will be started.

This study is divided into three stages: screening period, treatment period, and follow-up period. The screening period is 2-6 weeks after surgery. Treatment period: Subjects who meet the inclusion criteria but do not meet the exclusion criteria will receive postoperative intensive adjuvant therapy after signing the informed consent form. Follow up period: After stopping the study treatment, the subjects enter the follow-up period. Follow up period: Head MRI examination and evaluation will be conducted at baseline, postoperative, before radiotherapy, and after radiotherapy. MRI enhanced scans will be performed every month during the follow-up period to observe PFS until the end of the follow-up period. For subjects who have not withdrawn their informed consent form, survival information (i.e. date and cause of death, subsequent tumor treatment, etc.) will be collected every month through telephone and/or clinical visits.

This study is expected to have an enrollment period of 24 months and a follow-up period of 24 months.

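### Two dosing lines in protocol section 3.1 are wrong as written: the modified Stupp boost has a second dose where the number of fractions belongs, and adjuvant temozolomide cycle 1 carries two doses

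*Protocol*

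**What the plan says.** All the prescriptions are in protocol section 3.1, under the four treatment plans.

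- **Boost, modified Stupp group.** For residual lesions, or lesions that recur or progress early after surgery, "high-dose PGT 66Gy/30Gy will be given locally". The next sentence gives the other two volumes: "PTV1 in high-risk areas around the tumor bed will be 60Gy/30F, and in low-risk areas will be 54Gy/30F". The Stupp group has the same pair, 60 Gy and 54 Gy, each in 30 fractions.
- **Adjuvant temozolomide, Stupp group.** "The first cycle is 150mg/m² po qd on d1-5,28 days", followed directly by "Cycle 2-6: Cycle 1: 200mg/m² po qd for d1-5,28 days".
- **Adjuvant temozolomide, other three groups.** The two antibody groups say only that "TMZ combined with PD-1/VEGF dual antibody will be used as adjuvant therapy" and that "TMZ combined with PD-1/CTLA-4 dual antibody will be used as adjuvant therapy". The modified Stupp group says that "6 cycles of adjuvant TMZ chemotherapy will be started". None of the three gives a temozolomide dose of its own.
- **Background, section 1.3.** The rationale for treating residual disease more intensively speaks of "administering low-dose radiation to residual or recurrent lesions alone".

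**The concern.** These lines tell the site what to give. The boost is the only feature in section 3.1 that separates the modified Stupp arm from control, and its fractionation cannot be read from the text. The temozolomide line is the only adjuvant temozolomide dose in the shown text, and it attaches two doses to the same cycle.

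What is at stake is safe dosing and a clearly defined intervention. The protocol gives its own reason to care about the boost: radiation necrosis is a named secondary objective (2.2.2), and section 1.3 mentions side effects in high-dose areas as a possible reason why earlier dose escalation did not help. The arm most relevant to that objective has no stated dose per fraction for its boost.

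The text does not show that delivery would differ between patients or arms.

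**Working it through.** The plan gives no statistical figure to reproduce here. The check is a side-by-side reading, with simple arithmetic to show the size of the ambiguity.

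**1. Boost.** Inputs are the radiotherapy entries in section 3.1. Dose per fraction = total dose ÷ number of fractions.

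| Volume | As printed | Dose per fraction |
|---|---|---|
| High-risk area (both arms that list volumes) | 60Gy/30F | 60 ÷ 30 = 2.0 Gy |
| Low-risk area (same arms) | 54Gy/30F | 54 ÷ 30 = 1.8 Gy |
| Boost (modified Stupp) | 66Gy/30Gy | cannot be computed: no fraction count |

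Taken literally, the boost entry is a ratio of two doses, 66 ÷ 30 = 2.2 with no unit. No other part of the shown text gives its fractionation.

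**2. Adjuvant temozolomide.** Inputs are 150 and 200 mg/m² per day on days 1 to 5, and the six cycles stated for the Stupp and modified Stupp groups.

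- Cycle 1 under its first label: 150 × 5 = 750 mg/m².
- Cycle 1 under its second label: 200 × 5 = 1000 mg/m².
- Difference: 1000 − 750 = 250 mg/m²; 250 ÷ 750 = 33%.
- Six cycles, 150 mg/m² in cycle 1 and 200 mg/m² in cycles 2 to 6: 750 + 5 × 1000 = 5750 mg/m².
- Six cycles, 200 mg/m² throughout: 6 × 1000 = 6000 mg/m².
- Difference: 6000 − 5750 = 250 mg/m²; 250 ÷ 5750 = 4.3%.

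These percentages are illustrative. They measure the gap between the two labels, not a difference known to occur in practice.

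**3. Background wording (minor).** Section 1.3 calls the radiation to residual or recurrent lesions low-dose; section 3.1 calls it high-dose. The same paragraph of 1.3 treats 62.5 to 80 Gy as an increase over the standard 60 Gy, and the 66 Gy stated in 3.1 lies in that range.

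**The case against.** The strongest reply is that these are plain slips: one wrong or missing unit, and one surplus label after a clause that already names the first cycle. On that view there are no rival regimens, and the 33% and 4.3% describe a reading in which the explicit first-cycle clause is ignored. This is fair as far as it goes. The faults probably are slips, and the percentages are only illustrative. But the text does not show whether the stray label is surplus or the remnant of a lost clause, and a prescription should not have to be guessed.

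A second reply is that a figure within section 3.1 and the section 3.2 flowchart are not shown and may carry the missing values. This limit stands: statements about what is absent apply to the shown text only. It does not remove the fault, because a correct flowchart would then conflict with the prose. Nor does damage in text extraction explain it well. Both lines are in running prose, and the fraction notation came through correctly in the sentence next to the boost.

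A third reply concerns section 1.3: it is background, and low-dose there may be a loose translation for a modest or confined escalation. That is possible, so the point is kept as a minor one and the conclusion does not depend on it.

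**Conclusion.** The point holds. Two prescription lines in section 3.1 are wrong as written, and nothing else in the shown text resolves them. The boost of one of the four arms has no readable fractionation. The adjuvant temozolomide line, on which all four arms rely in the shown text, gives cycle 1 two doses.

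The conclusion assumes only that the shown prose is the current protocol text, and it is limited by the figures that could not be checked. Sample size and error rates are untouched. The sponsor should correct this on grounds of dosing safety and a clear definition of the interventions.

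**What to change.** By amendment to section 3.1, the sponsor should:

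- reconcile the boost entry and write it as total dose and number of fractions, in the format used for the other volumes;
- reconcile the temozolomide line so that each cycle carries one dose, and make clear that the other three arms refer to it, if that is the intention;
- align the wording of section 1.3 with section 3.1;
- check the figure in section 3.1 and the section 3.2 flowchart for the same entries.

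Which values are right is for the sponsor to settle; none is proposed here. If both faults are slips, the cost is a few lines of text, with no change to design, data or patient numbers. Whether it goes further cannot be known until the sponsor has reconciled the passages.

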3.2 Research and Design Flowchart

3.3 Study population

3.3.1 Inclusion Criteria

Patients eligible for this study must meet all of the following criteria:

- 1) Voluntary participation in clinical research: fully understand and be informed of this study, and sign a written informed consent form; Willing to follow and capable
 - Complete all experimental procedures.
- 2) Age: ≥ 18 years old, both male and female are acceptable.
- 3) Pathologically diagnosed GBM patients
- 4) Partial surgical resection or recurrence and progression 2-6 weeks after surgery (before radiotherapy)
- 5) Adequate organ and bone marrow function, without severe hematopoietic dysfunction, heart, lung, liver, kidney dysfunction, or immune deficiency:
 - a) Blood routine: Absolute neutrophil count (ANC) $\geq 1.5 * 10^9/L$ (1500/mm³), platelets $\geq 75 * 10^9/L$, hemoglobin ≥ 9 g/dL (if bone marrow is involved, platelets $\geq 50 * 10^9/L$, ANC $\geq 1.0 * 10^9/L$, hemoglobin ≥ 8 g/dL).
 - b) Liver function: Serum bilirubin ≤ 1.5 times the upper limit of normal value, aspartate aminotransferase (AST) and alanine aminotransferase (ALT) ≤ 1.5 times the upper limit of normal value (AST is allowed if there is liver involvement, ALT ≤ 5 times the upper limit of normal value).
 - c) Renal function: Serum creatinine ≤ 1.5 times the upper limit of normal value.
 - d) Coagulation function: INR ≤ 1.5 times the upper limit of normal value; PT and APTT are ≤ 1.5 times the upper limit of normal values (unless the subject is receiving anticoagulant treatment and PT and APTT are within the expected range of anticoagulant treatment at the time of screening).
- 6) Left ventricular ejection fraction (LVEF) $\geq 50\%$ in cardiac function examination.
- 7) The serum pregnancy test is negative, and effective contraceptive measures have been taken from the signing of the informed consent form until 6 months after the last chemotherapy.
- 8) Thyroid stimulating hormone (TSH), free thyroxine (FT4), or free triiodothyronine (FT3) are all within the normal range of $\pm 10\%$.
- 9) Ophthalmic examination: including dilated pupil fundus examination, slit lamp examination, and fundus color photography.

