7.1 Definition

AE refers to any adverse medical event that occurs from the signing of the informed consent form by clinical trial subjects until 90 days after the last use of the study treatment, regardless of whether there is a causal relationship with the trial treatment, and is determined as an adverse event.

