Adverse events leading to hospitalization or prolonged hospital stay in clinical studies should be considered as SAEs. Any first-time hospitalization by a medical institution meets this standard. Hospitalization does not include the following situations: rehabilitation institutions; Sanatorium; Routine emergency room admission; Same day surgery (such as outpatient/same day/non bedridden surgery); Hospitalization or prolonged hospital stay that is not related to the worsening of AE is not itself an SAE. For example, being admitted to the hospital due to an existing illness, without any new adverse events or worsening of the existing illness (such as in order to check for laboratory abnormalities that have persisted since before the experiment); Hospitalization due to management reasons (such as annual routine physical examinations); Hospitalization as specified in the trial protocol during clinical trials (such as operating according to the requirements of the trial protocol); Elective hospitalization unrelated to the worsening of adverse events (such as elective surgery); The scheduled treatment or surgical procedure should be recorded in the entire trial protocol and/or individual baseline data of the subjects.

Diagnostic or therapeutic invasive procedures (such as surgery) and non-invasive procedures should not be reported as adverse events (AEs). However, if the disease condition that led to this procedure meets the definition of AE, it should be reported. For example, acute appendicitis that occurred during the AE reporting period should be reported as an AE, and appendectomy performed as a result should be recorded as the treatment method for that AE.

5) SAE's reporting system

The reporting period for SAE should start from the signing of the informed consent form by the subjects and continue until 90 calendar days (including 90 days) after the last use of the study drug. If a serious adverse event (SAE) occurs, whether it is the first report or follow-up report, the researcher must immediately fill out the "New Drug Clinical Research Serious Adverse Event Report Form", sign and date it, and report it to the relevant provincial, autonomous region, or municipality drug regulatory department, NMPA (via EMS), health administrative department (via fax to the Medical Administration Bureau), notify the applicant (via email), and promptly report to the ethics committee within 24 hours of the researcher's knowledge.

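### The contraception window in inclusion criterion 7 runs from the last chemotherapy, so it does not count antibody doses given after the last temozolomide dose in two of the four arms

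*Protocol*

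**What the plan says.** Criterion 7 in section 3.3.1 of the Protocol asks for a negative serum pregnancy test and that "effective contraceptive measures have been taken from the signing of the informed consent form until 6 months after the last chemotherapy". It is one of a list that every patient must meet, with no arm-specific wording. It is also the only contraception rule in the visible text.

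Section 3.1 describes the arms. The Stupp and modified Stupp groups receive six adjuvant cycles of TMZ, which is called chemotherapy; for the modified group the wording is "6 cycles of adjuvant TMZ chemotherapy will be started". Adjuvant TMZ is given on days 1-5 of a 28-day cycle. In the other two arms:

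- "TMZ combined with PD-1/VEGF dual antibody will be used as adjuvant therapy", dosed as "PD-1/VEGF dual antibody 20mg/kg intravenous infusion once, with a cycle of 21 days".
- "TMZ combined with PD-1/CTLA-4 dual antibody will be used as adjuvant therapy", dosed as "PD-1/CTLA-4 dual antibody 6mg/kg intravenous infusion once, with a cycle of 14 days".

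The antibodies are not called chemotherapy, and the visible text gives no number of antibody cycles and no stopping date.

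The safety-reporting windows use a wider anchor. Section 7.1 collects adverse events "until 90 days after the last use of the study treatment", and section 7.6 sets the serious adverse event period to "90 calendar days (including 90 days) after the last use of the study drug".

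**The concern.** The end of the contraception window depends on one component of treatment, while two arms contain a second component on a different cycle. If the antibody is the last drug given, a patient of reproductive potential can follow criterion 7 exactly and still have less than 6 months of contraception after her or his last study drug.

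The wider anchor in sections 7.1 and 7.6 does not contradict criterion 7, because those windows serve another purpose. It does show that suitable wording already exists in the protocol. What is at stake is a small gap in participant protection. The two TMZ-only arms are unaffected.

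**Working it through.** The protocol states no figure here to reproduce, so the check is a count of dosing days.

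**Inputs from section 3.1**
- Adjuvant TMZ on days 1-5 of each 28-day cycle.
- Six adjuvant cycles, stated for the Stupp and modified Stupp groups.
- Antibody every 21 days (PD-1/VEGF) or every 14 days (PD-1/CTLA-4).

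**Assumptions**
- Six TMZ cycles in the antibody arms as well.
- First antibody dose on adjuvant day 1, and no delays.
- 6 months = 183 days. The shortfalls do not depend on this choice.

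**Formulas**
- Last TMZ dose after *n* cycles = (*n* − 1) × 28 + 5.
- End of contraception = last TMZ dose + 183.
- Antibody dose *k* falls on day 1 + 21(*k* − 1) or 1 + 14(*k* − 1).
- Cover = end of contraception − last antibody dose. Shortfall = 183 − cover.

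**Full TMZ course.** Last TMZ dose = 5 × 28 + 5 = day 145. End of contraception = 145 + 183 = day 328. Six TMZ cycles last 168 days, which is exactly 8 × 21 and 12 × 14.

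| Scenario | Schedule | Last antibody dose | Cover | Shortfall |
|---|---|---|---|---|
| (a) Antibody to end of TMZ cycle 6 | 21-day, 8 doses | 1 + 21 × 7 = 148 | 328 − 148 = 180 | 3 days |
| (a) Antibody to end of TMZ cycle 6 | 14-day, 12 doses | 1 + 14 × 11 = 155 | 328 − 155 = 173 | 10 days |
| (b) Six antibody cycles only | 21-day | 1 + 21 × 5 = 106 | 328 − 106 = 222 | none |
| (b) Six antibody cycles only | 14-day | 1 + 14 × 5 = 71 | 328 − 71 = 257 | none |

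The crossover is the 8th dose on the 21-day cycle, since the 7th falls on 1 + 21 × 6 = day 127. On the 14-day cycle it is the 12th, since the 11th falls on 1 + 14 × 10 = day 141. Any course at least that long ends after the last TMZ dose on day 145.

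**(c) TMZ stopped early, antibody still given to day 168** (conditional; the text neither states nor excludes it)

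| TMZ stopped after | Last TMZ dose | End of contraception | Cover, 21-day / 14-day | Shortfall, 21-day / 14-day |
|---|---|---|---|---|
| Cycle 5 | 4 × 28 + 5 = 117 | 300 | 152 / 145 | 31 / 38 days |
| Cycle 3 | 2 × 28 + 5 = 61 | 244 | 96 / 89 | 87 / 94 days |

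The protocol does not say how many patients any of these cases would affect.

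**The case against.** The strongest objection is that the antibody duration decides whether there is a gap at all, and that it may be given in the figure or flowchart missing from the text available here. If the limit is six antibody cycles, scenario (b) applies and nothing is short. This stands: the visible text does not choose between (a) and (b), so a gap is possible but not shown to occur.

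Second, under (a) the difference is 3 or 10 days. It counts as short only if the chemotherapy standard of 6 months is applied to the antibodies, for which the protocol states no period of their own. This also stands, and so no claim is made that the remaining 180 or 173 days are inadequate.

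Third, scenario (c) has thin support. Section 3.3.3 speaks of stopping treatment as a whole. The serious adverse event handling at the end of section 7.6 allows the drug to be stopped or reduced, but does not say whether one agent may continue alone. Those figures are therefore illustrations only.

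Fourth, there are partial safeguards. Section 3.3.2 excludes pregnant and lactating women, and section 3.3.3 requires treatment to stop on a positive pregnancy test. They limit exposure during treatment but do not extend the window after it.

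Finally, the word chemotherapy may have been meant loosely, for the whole adjuvant regimen. Section 3.1 does not use it that way; if that was the intent, the change only makes it explicit.

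**Conclusion.** The concern holds as a minor wording defect. One rule covers all arms, and its anchor leaves out a study drug that can be the last one given. Under plain co-administration to the end of six TMZ cycles the shortfall is 3 days (21-day antibody) or 10 days (14-day antibody). It is zero if antibody treatment is limited to six cycles, and longer only if the antibody outlasts TMZ. These sizes rest on six TMZ cycles in the antibody arms, antibody from adjuvant day 1 and no dosing delays. Confidence is moderate, because the antibody duration is not visible. The change is optional but worth making at its low cost.

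**What to change.** In criterion 7, replace the reference to the last chemotherapy with: the last dose of any study drug (TMZ or antibody, whichever is later). Keep the 6 months; the protocol gives no basis for a different length for the antibodies. Check that the participant information, not visible here, says the same.

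The new wording is right for whatever antibody duration the study schema sets. The cost is one phrase and one consistency check, plus a somewhat longer contraception requirement for some antibody-arm patients: 3 or 10 days under plain co-administration.
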